5. STUDY DESIGN

This study is a within-subject cross-over trial design to assess the glycemic response of fibre enriched rice consumer by human subjects as compared to normal non-enriched rice in a mixed meal setting. The approximate time to complete study recruitment will be 4 weeks. Generally healthy population will be recruited in this study. There will be 3 visits in total (including screening). Each visit last from 3-4 h. During the visit, the participants are required to undergo a mixed meal tolerance test and carry a continuous glucose monitoring system for the next 14 days. The meals will be prepared by caterer in the morning of the test and send to the participants. The participant's glycemic response to control (normal rice) will be compared to their response after consumption of fibre enriched rice in a mixed meal setting. A reduction in postprandial blood glucose response will show that Fibre Grain rice is effective in improving the glycemic response of a meal.

6. STATISITCAL METHODS

The sample size was calculated based on Glycaemic Index Research Report #1719 conducted by Sydney University's Glycaemic Index Research Service on the 30% Fibre Grain replacement.

Based on the primary outcome of detecting a difference of 27 units in incremental area under the curve (iAUC) from 0 to 120 minutes (iAUC 0-120min) between control and 30% fibre enriched rice and a standard deviation of 25 units in iAUC 0-120min, calculations showed that with $\alpha = 0.05$, and power of 0.9, at least 21 subjects were needed. To account for possible subject attrition during the study, 25 subjects were recruited.

All data will be analyzed using statistical software (eg. SPSS/Stata), with significance defined as a p value of less than 0.05 on a 2-sided paired t-test. Other variables will be presented as mean \pm SE with differences between groups assessed by mixed model for categorical variables and continuous variables. Data will be explored for assessment of errors, missing values, and distribution of the variables. Evaluable subjects will be those who meet eligibility and have no missing values for calculating area under the curve (AUC). Variables that will be obtained include:

For CGM profile, paired t-test will be used to compare the fibre enriched rice meal and normal rice meal group in the following:

- a. Mean of interstitial glucose (IG) per 24 hours
- b. Postprandial peak IG (highest level after meal at breakfast, lunch and dinner)
- c. Postprandial time to peak IG (at breakfast, lunch and dinner)
- d. Mean amplitude of glycemic excursion (MAGE) to assess variability. This is determined by calculating arithmetic mean of the difference between qualifying consecutive peak and nadirs. Glucose excursions > 1 SD of the mean glucose concentrations will be included.

For postprandial glucose profile after the single meal:

- a. Plasma fasting and postprandial glucose (mmol/l), insulin (mU/l) and gut hormones.
- b. The incremental AUC (0-2h) will be derived from the glucose concentration profile during the meal test (defined as the area under the glucose curve that is over the basal value taken at time). Differences between the two meals will be analyzed by paired t-test

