4. TRIAL SCHEDULE

4.1. Study Visits and Procedures

(a) Visit 1 - Screening

Volunteers will be interviewed and screened by study personnel. If the volunteer satisfies the inclusion and exclusion criteria, a written informed consent will be obtained from all selected volunteers prior to their participation in the study. Volunteers will have the study explained to them by a study personnel, will read the consent form, have the opportunity to ask questions, and then sign the approved written Informed Consent form and keep a copy. The study personnel will then proceed to schedule visit 2 and 3 with the participant.

(b) Visit 2 - Installation of CGMS (Day 1)

Upon arrival, the participant will be educated on how to maintain and care for a CGMS and to keep a food and activity diary for the duration of the CGM. During this period (Day 1-14), participants will receive SMS to check on the CGMS. If there is a need, the research personnel will arrange for a mutually convenient time and place to review and replace the CGMS. Then, the participants will proceed to take the first MMTT.

Mixed meal tolerance test (MMTT)

Before the test, measurement of participants' height, BMI, waist and hip circumference, will be done and recorded. Next, participants will be asked to attend the MMTT protocol. The participant will need to fast (no food or drinks, except plain water) from 10 pm the night before or for approximately 10-12hr prior to the study visit. No food except clear water should be

consumed. A cannula will be inserted into the participant's forearm and the cannula will remain for blood sampling only. A fasting sample will be taken for the immediate measurement of glucose while other samples for insulin, gut hormones (GLP-1, GIP, Peptide YY, Ghrelin, and Glucagon), and other metabolites will be taken, processed, stored and analysed in batches at a later stage. Then, the participant will be given either mixed meal with controlled rice or mixed meal with test rice. At 0, 15, 30, 45, 60, 90, 120 minutes, blood will be sampled through a cannula from one of the arms. Subjects will be asked to remain seated throughout the visit and only minimal movement is allowed. Blood-taking will be conducted in room designated and approved for phlebotomy purposes. Only trained personnel and/or trained nurses will be conducting the blood drawn.

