At each time point, the participant will also be given a visual analogue scale (VAS) to indicate how they feel in response to given statements by marking an "X" on a 100-mm line. For example, "How strong is your desire to eat? " Response: Very weak (0 mm) to very strong (100 mm). Appetite was evaluated using a 100 mm VAS. At time 15 min, palatability of the treatment will be assessed by five characteristics, from bad (0 mm) to good (100 mm). These characteristics were visual appeal, smell, taste, texture, and overall pleasantness of the meal given. Scores were determined by measuring the distance (in mm) from the left starting point of the line to the intersection of the "X". The average scores and AUC will be calculated and compared between the two meals

(c) Continuous glucose monitoring (Day 1 - 14)

For the next 14 days, participants will be provided with lunch and dinner from the research team through delivery. They will be randomized to receive either mixed meal with controlled rice or mixed meal with Fibre Grain rice for day 1 to 7 and received the alternative for the day 8- 14. Participants will not be told whether they are receiving the Fibre Grain rice or control rice

(d) Visit 3 (Day 14 of CGM) – MMTT2 and removal of CGMS

On day 14, participants will return to undergo the second MMTT. Their height, BMI, waist and hip circumference will be measured and recorded. Participants will be asked to attend the same MMTT protocol (refer to Day 1 – MMTT protocol). Lastly, they will return the CGMS, and your 14-day food and activity diary

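### The evaluable rule removes a participant's whole pair for one missing glucose value out of 14, and the 25-for-21 allowance does not budget for that loss

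*Combined protocol and SAP*

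**What the plan says.** Section 6 defines who is analysed: "Evaluable subjects will be those who meet eligibility and have no missing values for calculating area under the curve (AUC". The primary endpoint is glucose iAUC over 0 to 120 min, "defined as the area under the glucose curve that is over the basal value taken at time", compared between meals by a two-sided paired t-test.

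Section 4.1(b) sets the sampling: "At 0, 15, 30, 45, 60, 90, 120 minutes, blood will be sampled through a cannula from one of the arms". Section 4.1(d) repeats it at visit 3: "Participants will be asked to attend the same MMTT protocol". A complete pair is therefore 7 × 2 = 14 glucose values. Section 4.1(b) also says "A fasting sample will be taken for the immediate measurement of glucose"; if that draw is separate from the 0-min draw, the count is 16.

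The sample size rests on "detecting a difference of 27 units in incremental area under the curve (iAUC) from 0 to 120 minutes" and "a standard deviation of 25 units in iAUC 0-120min", giving at least 21 subjects. Section 6 recruits 25 to allow for attrition. Section 3.6 gives the minimum as 20 and recruits a new subject only below 20.

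No section gives an interpolation or imputation rule, a minimum number of points per curve, or an expected rate of missed samples. Section 10.2 repeats the general analysis text without the evaluable rule.

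**The concern.** The comparison is paired, so one spoiled tube at 60 min in one visit discards 13 valid values, including a complete curve from the other visit. An area built from straight lines between time points does not need every interior point, so the rule discards pairs from which the endpoint can be derived. The loss accumulates over 14 draws and adds to drop-out, which is the only loss the plan allows for.

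There is a smaller ambiguity. The rule does not say which AUC it means, and the VAS paragraph in Section 4.1(b) plans one too: "The average scores and AUC will be calculated and compared between the two meals".

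At stake are usable pairs for the primary endpoint, and a gap in pre-specification that would have to be filled after the data are seen if anyone wished to recover those pairs.

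**Working it through.** **1. The plan's own 21.** Inputs from Section 6: difference 27, SD 25, two-sided alpha 0.05, power 0.90, paired t-test. The plan does not say whether 25 is the SD per meal or of the paired difference.

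- Per meal, uncorrelated meals: SD of difference = 25 × √2 = 35.4 and effect = 27 / 35.4 = 0.76. Noncentral-t power is 0.899 at 20 and 0.914 at 21, so N = 21. This reproduces the plan.
- SD of the difference: effect = 27 / 25 = 1.08 and N = 12. This does not reproduce 21.

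**2. Evaluable participants.** Let p be the chance that any one draw is missing. The documents give no value, so p is an assumption. With independent misses and no drop-out, P(evaluable) = (1 − p)^14 as written. If one missing interior value per curve is tolerated, it is [(1 − p)^7 + 5p(1 − p)^6]². The number evaluable is Binomial(25, that probability).

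| p per draw | Not evaluable, as written | Expected of 25 | P(≥21), as written | P(≥21), one interior gap allowed |
|---|---|---|---|---|
| 0.5% | 7% | 23.3 | 0.98 | >0.99 |
| 1% | 13% | 21.7 | 0.78 | >0.99 |
| 2% | 25% | 18.8 | 0.23 | 0.94 |

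With two ordinary drop-outs (23 left) and p = 1%, the chance of keeping 21 is 0.40 as written and 0.93 with the gap allowed.

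**3. Power.** Difference 27, two-sided alpha 0.05:

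| Pairs | SD of difference 35.4 | SD of difference 25 |
|---|---|---|
| 21 | 0.914 | 0.997 |
| 20 | 0.899 | 0.996 |
| 18 | 0.863 | 0.991 |
| 16 | 0.814 | 0.981 |

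Averaged over the number evaluable from 25 with no drop-out, power at SD of difference 35.4 is 0.92 at p = 1% and 0.87 at p = 2%.

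**4. What bridging costs.** Section 6 names no area method, so the trapezoid is assumed here. I also assume that the plan's unlabelled units are mmol/L × min. Dropping an interior point changes the area by (interpolated value − true value) × half the time between its neighbours. Two assumed curves (mmol/L at 0, 15, 30, 45, 60, 90, 120 min):

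- Curve A: 4.8, 5.6, 7.0, 7.4, 6.9, 6.1, 5.5; iAUC 180.75. Missing 30 min: (6.5 − 7.0) × 15 = −7.5 units (−4.1%). Missing 45 min: (6.95 − 7.4) × 15 = −6.75 units (−3.7%). The other three points: 0.8% to 2.5%.
- Curve B, sharper: 4.8, 6.2, 8.0, 7.0, 6.2, 5.6, 5.2; iAUC 163.5. Missing 30 min, the peak: (6.6 − 8.0) × 15 = −21 units (−12.8%). The other four points: 0.9% to 4.6%.

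A missing 0- or 120-min value has a neighbour on one side only and cannot be bridged.

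**The case against.** The complete-curve rule is pre-specified and leaves no room for judgement, and retention against accuracy is a trade-off. Four points on that side have force.

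- **The rate is unknown.** At 0.5% per draw there is no practical problem.
- **Independence is unlikely.** All draws in a visit come through one cannula, so failures probably cluster. For a given p, clustering affects fewer participants. It also leaves runs of missing values that a one-gap rule cannot rescue. The table in step 2 therefore probably overstates both the loss and the recovery.
- **Section 3.6 is a possible backstop.** If non-evaluable completers count as lost, recruitment resumes below 20, where power is still 0.899 on the less favourable reading. The text does not say whether they count.
- **Bridging is not free.** A lost peak can cost 21 units in one person against a 27-unit target. The error runs in one direction, since losing a peak always shrinks the curve.

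These limit the size of the point and shape the remedy. They do not justify discarding a pair whose 60- or 90-min value alone is missing.

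A reader might infer more than the documents support. One inference is that the rule leaves the trial underpowered: that needs a miss rate that the plan does not give, and the power loss is modest on one reading of the SD and negligible on the other. Another is that a missed appetite mark disqualifies a participant for glucose: the only AUCs named in Section 6 are glucose iAUCs, so this is wording to clarify, not the likely meaning. A third is that any interior point can be bridged with little error: step 4 shows otherwise near the peak.

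**Conclusion.** The point stands as a correctable weakness in the analysis rule. As written, one missing glucose value out of 14 removes a pair from the primary comparison, nothing in the documents relaxes this, and the recruitment allowance does not count it. Under assumed independent misses without drop-out, the chance of keeping 21 of 25 falls from 0.98 to 0.23 as the per-draw rate rises from 0.5% to 2%; clustering would soften this.

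The consequence is mainly lost precision. Relative to 21 pairs, power falls by about 1.5 points at 20 and 5 points at 18 if 25 is the per-meal SD with uncorrelated meals. If 25 is the SD of the difference, power is still 0.98 at 16. The change is worth making before data are seen; the design does not depend on it.

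**What to change.** Replace the evaluable sentence in Section 6 with:

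> A participant is evaluable for the primary endpoint if, at both MMTTs, the 0- and 120-min glucose and at least 4 of the 5 intermediate values are available. A single missing intermediate value is bridged by the trapezoid between its neighbours, except that a missing 30- or 45-min value (near the expected peak) is imputed by a pre-specified model using the participant's other values and the same-meal time profile. Evaluability is judged separately for each analyte and for VAS.

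Report the complete-sample set as a sensitivity analysis. State in Section 3.6 whether a completer who is not evaluable counts towards replacement, and reconcile its 20 with the 21 in Section 6.

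The cost is a few sentences and one imputation model to specify. The downside is some iAUC error in participants with a filled point. On the assumed curves plain bridging costs about 1% to 5% away from the peak and about 4% to 13% at it, which is why the 30- and 45-min samples are treated separately. The sensitivity analysis would show whether filled values drive the result.

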3.6. Subject Replacement

To account for the dropout rate, 25 participants will be recruited for minimal sample size of 20 subjects. A new subject will only be recruited if number of subjects drop below 20.

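### Read as written, the AUC-based evaluable-subject rule in Section 6 would drop usable CGM pairs from CGM endpoints that use no AUC

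*Combined protocol and SAP*

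**What the plan says.** Section 6 contains the only definition of an analysis set in the document: "Evaluable subjects will be those who meet eligibility and have no missing values for calculating area under the curve (AUC". The next words, "Variables that will be obtained include", introduce two lists. The CGM list comes first and opens with "For CGM profile, paired t-test will be used to compare the fibre enriched rice meal and normal rice meal group in the following". Its items are "Mean of interstitial glucose (IG) per 24 hours", "Postprandial peak IG (highest level after meal at breakfast, lunch and dinner", "Postprandial time to peak IG (at breakfast, lunch and dinner" and the mean amplitude of glycemic excursion (MAGE). The single-meal list follows and includes the 0-2 h incremental AUC of meal-test glucose.

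Section 4.1 sets out the data collection. Each mixed meal tolerance test (MMTT) has seven blood samples, at 0, 15, 30, 45, 60, 90 and 120 minutes. The sensor runs over Days 1-14, with one rice on Days 1-7 and the other on Days 8-14. For the last visit it says: "On day 14, participants will return to undergo the second MMTT". The sensor is returned at that same visit. Section 4.1 also plans an AUC for the appetite scales completed during the meal tests.

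Section 10.2 repeats the general analysis text but defines no set. No section gives a CGM set, a minimum amount of sensor data, or an exemption of the CGM endpoints from the AUC rule.

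**The concern.** The rule asks for data that the CGM endpoints do not use. A paired comparison of CGM summaries needs sensor data under both rices. It does not need a complete set of meal-test samples.

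The likeliest affected case is ordinary: a participant attends both meal tests, a cannula fails or one draw is missed at either of them, and the sensor record is intact in both weeks. Under the literal rule that person is not evaluable, and a complete within-person CGM pair is discarded.

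The CGM comparison is the trial's only evidence on rice eaten repeatedly over days, and at most 25 pairs are planned. If the set is left as it stands, the team either loses pairs without reason or decides which participants to count once the data are in hand.

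**Working it through.** **The plan's own figure.** Section 6 states that at least 21 subjects are needed for a difference of 27 iAUC units, SD 25, two-sided alpha 0.05 and power 0.90. With SD 25 per meal and zero within-person correlation, the SD of the difference is 25 × √2 = 35.36. The exact paired t-test then has power 0.899 at n = 20 and 0.914 at n = 21, so 21 is reproduced. If 25 is instead the SD of the paired difference, n = 12. The present point does not depend on which was meant: the figure concerns the primary iAUC, and there is no equivalent calculation for CGM.

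**What the rule requires against what the endpoints use.**

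| Item | Data needed |
|---|---|
| Evaluable subject (Section 6), glucose AUC | 7 samples × 2 meal tests = 14 values |
| CGM 24-hour mean, peak, time to peak, MAGE | Sensor data in Days 1-7 and in Days 8-14 |

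The two requirements do not overlap. The rule does not say which AUC it means. If it also covers the appetite-scale AUC, still more values must be complete.

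**How many could be affected.** The documents give no rate of missed samples. Assume independent missingness with probability p per sample, so the chance of a complete record is (1 − p)^14:

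- p = 0.5%: 0.932, or 23.3 of 25 (about 1.7 lost)
- p = 1%: 0.869, or 21.7 of 25 (about 3.3 lost)
- p = 2%: 0.754, or 18.8 of 25 (about 6.2 lost)

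The first two rates correspond roughly to losing 1 to 3 pairs. The third passes the floor of 20 in Section 3.6 ("To account for the dropout rate, 25 participants will be recruited for minimal sample size of 20 subjects") and only shows how sensitive a 14-value rule is.

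**Effect on precision.** The half-width of the 95% CI for a paired mean difference is t(0.975, n−1) × SD/√n. The SD cancels in the ratio to n = 25. Suppose that all 25 have usable CGM pairs:

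| Pairs | t(0.975, n−1) | t/√n | Ratio to 25 |
|---|---|---|---|
| 25 | 2.064 | 0.413 | 1.000 |
| 24 | 2.069 | 0.422 | 1.023 |
| 23 | 2.074 | 0.432 | 1.048 |
| 22 | 2.080 | 0.443 | 1.074 |
| 20 | 2.093 | 0.468 | 1.134 |

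**Effect on power, purely as an illustration.** No CGM effect, SD or power target is planned. A standardised paired difference of 0.676 gives 90% power at 25 pairs. The same difference gives 89% at 24, 87% at 23, 86% at 22 and 82% at 20 (noncentral t, two-sided alpha 0.05).

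**The case against.** The best defence is that the exclusion is inferred. Section 6 never says in words that the CGM analyses are limited to evaluable subjects. Its wording could mean evaluable for the AUC analysis, and software running a paired t-test on a CGM summary would by default use everyone with both values. This is why the point is put as what the text does when read as written. It does not remove the problem, because this is the only set defined and both lists follow it. The mixed model named for other variables does not help either, since the CGM endpoints are assigned a paired t-test.

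Several stronger readings are tempting, and the documents do not support them:

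- *The rule governs every endpoint.* It stands before the two variable lists. The primary iAUC is named earlier in Section 6, and the appetite scales are in Section 4.1.
- *Week-2 withdrawals are the main loss.* The sensor is handed back at the visit with the second meal test, and no other return route is described. Someone who leaves in week 2 may have incomplete sensor data anyway.
- *All of the planned attrition is a loss due to this rule.* A participant who leaves before Day 8 has no CGM pair under any definition. Twenty pairs requires all five losses to have usable sensor data in both weeks.
- *The CGM result is biased.* Bias would need missing meal-test values to be related to the within-person CGM difference. Nothing in the documents links completion of the Day 14 test to tolerance of the second rice week.
- *A participant with both meal tests complete but one sensor week lost distorts the result.* Whatever the label, that person contributes nothing to a paired t-test.

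**Conclusion.** The point holds as a stated rule that does not fit the endpoints listed under it. Its effect is lost precision in the CGM comparison. The primary iAUC analysis does not change, and no bias is shown.

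The size is modest under plausible counts: about 2% to 7% on the width of the CGM intervals for 1 to 3 lost pairs. The 13% figure for 5 lost pairs is an upper bound in terms of the plan's own allowance from 25 down to 20. These figures assume that all 25 participants have usable CGM data in both weeks and that the rule is applied literally. The number of pairs lost is an assumption, because the documents give no missing-data rate. The change is worth making because the loss is avoidable at almost no cost.

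**What to change.** In Section 6, replace the single definition with one set per group of endpoints:

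- **Meal-test glucose iAUC:** eligible participants with a derivable iAUC at both MMTTs.
- **CGM endpoints:** all eligible participants whose sensor data meet a prespecified minimum in both rice weeks, whether or not the MMTT data are complete.

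The minimum amount of sensor data per week has to be written down before the data are examined. The plan has none at present, and without it membership of the CGM set would remain open to choice afterwards. State which AUC the completeness rule refers to, and report the number of pairs for each endpoint.

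The cost is a few sentences and no new data collection. The small downside is that denominators will differ between the MMTT and CGM tables, which the reported pair counts make clear.

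### CGM endpoints (secondary): meal peak and time to peak have no post-meal window, and the CGM days that count are not defined

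*Combined protocol and SAP*

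**What the plan says.** Section 6 gives four CGM endpoints: 24-hour mean interstitial glucose, meal peak, time to peak, and MAGE. They are compared between rices by paired t-test. The peak is defined as "Postprandial peak IG (highest level after meal at breakfast, lunch and dinner". The only post-meal window in the plan, 0-2 h, belongs to the glucose iAUC of the MMTT. The section names no CGM days and no period term.

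The schedule is in Section 4.1:
- The sensor is fitted at "Visit 2 - Installation of CGMS (Day 1", where participants are also told "to keep a food and activity diary for the duration of the CGM". At the same visit, "Then, the participants will proceed to take the first MMTT".
- The MMTT follows a fast "from 10 pm the night before or for approximately 10-12hr prior to the study visit". Section 5 puts each visit at 3-4 h.
- During CGM, "participants will be provided with lunch and dinner from the research team through delivery". Breakfast is not supplied.
- The rice assignment runs as control or "Fibre Grain rice for day 1 to 7 and received the alternative for the day 8- 14".
- The second MMTT is on Day 14. "Lastly, they will return the CGMS" at the end of that visit.

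Section 6.1 describes randomisation of the MMTT order and, additionally, of the CGM order. It states no link between them and no blocking or other balancing.

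**The concern.** **Post-meal window.** With no end time, the highest reading after lunch may come from an afternoon snack. That moves the time to peak and can hide a difference in the response to lunch itself. The diary could supply meal and snack times, but no rule uses it. Breakfast counts as an endpoint meal although participants choose it themselves, and the plan does not say whether the three meals are pooled.

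**Evaluable days.** If the supply periods serve as analysis periods, Day 1 contributes daytime and evening only, while Day 14 contributes mostly the overnight fast. The 24-hour mean could then differ between periods for reasons unrelated to rice. Each of these days also holds an MMTT meal that may be the opposite rice.

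At stake is how clearly the CGM results can be read, and how much choice is left until the data have been seen. CGM is the plan's only glucose measurement beyond a single test meal.

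**Working it through.** **The plan's own figure.** No sample size, SD or power is given for CGM. The stated N = 21 is for the MMTT iAUC. A two-sided paired t-test with a difference of 27 and an SD of the difference of 25 x sqrt(2) (25 per condition, zero correlation assumed) gives n = 21: power is 0.914 at 21 and 0.899 at 20. Nothing below enters that calculation.

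**1. Open-ended peak.** An illustration with invented curves: true peak difference -0.5 mmol/L, and snacks starting 2-4 h after the meal.

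| Snack frequency | Difference, 2-h window | Difference, 6-h window | Control time to peak, 2 h | Control time to peak, 6 h |
|---|---|---|---|---|
| 0% | -0.48 | -0.49 | 47 min | 47 min |
| 30% | -0.49 | -0.43 | 47 min | 67 min |
| 60% | -0.49 | -0.36 | 47 min | 87 min |

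The snacks were placed after 2 h, so the 2-h window is protected by construction. The table shows the mechanism; it does not predict a size.

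**2. Part days, if Days 1-7 and 8-14 are used.** A fast from 10 pm for 10-12 h implies a visit start of 8-10 am (inferred), and a visit of 3-4 h ends at 11 am-2 pm. Day 1 records 24 - 10 = 14 h to 24 - 8 = 16 h. Day 14 records 8 + 3 = 11 h to 10 + 4 = 14 h. Overnight is taken as midnight to 8 am (assumption), so six full days hold 144 h, of which 96 h are waking.

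Waking share with all readings pooled:
- 8 am, 3 h: 112/160 = 70.0% vs 99/155 = 63.9%, gap 6.1 points
- 8 am, 4 h: 112/160 = 70.0% vs 100/156 = 64.1%, gap 5.9
- 10 am, 3 h: 110/158 = 69.6% vs 101/157 = 64.3%, gap 5.3
- 10 am, 4 h: 110/158 = 69.6% vs 102/158 = 64.6%, gap 5.1

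Waking share with daily means averaged: Days 1-7 give (6 x 2/3 + 1)/7 = 71.4%. Days 8-14 give from (4 + 3/11)/7 = 61.0% to (4 + 6/14)/7 = 63.3%. The gap is 8.2-10.4 points.

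Per assumed 1 mmol/L waking-overnight difference, the period shift is therefore about 0.05-0.06 mmol/L (pooled) or 0.08-0.10 mmol/L (daily means). It scales in proportion: at 0.5 or 1.5 mmol/L the pooled shift is about 0.03 or 0.08-0.09.

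**3. How much reaches the rice contrast.** In a paired comparison without a period term, the share is |n1 - n2|/N, where n1 and n2 are the sequence sizes.
- Split 13:12: 1/25 = 4%, so 0.04 x 0.05 to 0.04 x 0.10 = 0.002-0.004 mmol/L.
- Simple 1:1 randomisation, average for odd N = C(N-1, (N-1)/2)/2^(N-1): 2,704,156/16,777,216 = 16% at N = 25 and 184,756/1,048,576 = 18% at N = 21, so 0.16 x 0.05 to 0.18 x 0.10 = 0.008-0.018 mmol/L.

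The rest is spread: near balance, a shift s adds about s squared, 0.0025-0.010 (mmol/L) squared, to the variance of the paired difference. The documents give no CGM SD to set this against.

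**4. MMTT meals.** Take an all-meal mean in which breakfast is unaffected by rice (assumption). Days 1-7 hold 14 supplied meals, 6 breakfasts and 1 MMTT = 21. Days 8-14 hold 12, 6 and 1 = 19. The retained share of the contrast is:
- orders match: 0.5 x 15/21 + 0.5 x 13/19 = 69.9%
- orders opposite: 0.5 x 13/21 + 0.5 x 11/19 = 59.9%
- independent 1:1 orders, average: 64.9%
- MMTT days left out: 12/18 = 66.7%

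The average loss is 66.7 - 64.9 = 1.8 points. Lunch and dinner analysed on their own lose nothing.

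**5. Day 8.** Days 2-7 vs 8-13 equalises clock hours. But the hours of Day 8 before lunch follow the Day 7 dinner with the other rice, and no washout is stated. Only the second period has this problem. Days 3-7 vs 9-13 avoids it.

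**The case against.** The strongest reply is that Section 6 never makes Days 1-7 and 8-14 the analysis windows. They are supply periods, and a mean per 24 hours can naturally be read as one over complete days. This stands. A reader might infer that the plan mixes part days into the CGM results; the documents support only that it does not say which days count. The phrase also belongs to one endpoint and does not settle the days for the other three.

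Second, a reader might infer a biased rice comparison. The part-day shift is a period effect. It largely cancels when sequences are near balance and mainly adds a little noise. The reply is weaker without stated balancing, but even then the amounts are small.

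Third, the MMTT dilution arises only where meals are pooled, and the plan does not define a pooled meal endpoint. If the two orders matched, leaving out the MMTT days would lower the retained contrast (69.9% to 66.7%). This also stands.

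Fourth, no MAGE distortion has been calculated, so none is claimed.

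Fifth, the diary already exists and 0-120 min is only one reasonable window. True, but a rule for using the diary and a choice of window are what is missing. No part of the reply removes the open-ended peak.

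**Conclusion.** The point holds as a minor one, for the CGM endpoints only. They are treated as secondary because the iAUC is named as the primary outcome. Its firmest part is the missing post-meal window: under the definition as written, a later snack can set both peak and time to peak. How often that would happen cannot be judged from the documents.

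The undefined days matter less. If the supply periods were used, the artefact would be about 0.05-0.10 mmol/L between periods, and about 0.002-0.004 (13:12 split) to 0.008-0.018 mmol/L (average under simple randomisation) in the rice contrast. These figures rest on inferred visit times, an assumed 8-h night and an assumed 1 mmol/L waking-overnight difference. The primary analysis and its sample size do not change.

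**What to change.** Amend the CGM part of Section 6:

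1. Analyse peak and time to peak meal by meal in one fixed window, for example 0-120 min as for the MMTT iAUC. Take meal start from the food diary and cut the window at the next eating occasion recorded there. Make supplied lunch and dinner on Days 2-7 vs 8-13 (12 vs 12 meals) the main meal endpoints. Report breakfast separately on Days 3-7 vs 9-13.
2. Compute the 24-hour mean and MAGE on complete days without an MMTT, Days 3-7 vs 9-13, so that no day follows a dinner with the other rice. Keep Days 2-7 vs 8-13, and all days, as sensitivity analyses.
3. Add a period term to the paired crossover comparison.

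**Cost.** This is wording only, using sensor and diary data already planned. The 24-hour mean and MAGE rest on 5 vs 5 days. Against 6 vs 6, the within-person day-to-day variance rises by (1/5 + 1/5)/(1/6 + 1/6) = 1.20, or 20%, if days are independent. For supplied meals, going from about 14 vs 12 to 12 vs 12 gives (1/12 + 1/12)/(1/14 + 1/12) = 1.077, about 8% more within-person meal variance if meals are independent. The period term costs one degree of freedom: the critical t rises from 2.064 to 2.069 at N = 25 and from 2.086 to 2.093 at N = 21, or 0.2-0.3%.
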